- 1) **Personalized Genomic Testing for Skin Cancer – Maximizing Utility and Reach – 05/16/17**
- (v. 10)
- 2) **IRB Review History N/A**
- 3) **Objectives**

This study will have two phases, with an added usability test after Phase I and before Phase 2. Phase 1: Cognitive Interviews in Spanish.

Phase 2: Personalized Genomic Testing for Skin Cancer (PGT-SC).

The overarching goal of this study is to learn more about how to maximize the availability, comprehension and appropriate uptake of personalized genomics among different populations in New Mexico. The proposed study has been funded as an R01 by NCI for three years.

Aim I: To examine the personal utility (that is, how does personal genomic testing help the individual) of Personal Genomic Testing for Skin Cancer (PGT-SC) in terms of short-term (three months after testing) sun protection, skin screening (i.e., behaviors), communication, melanoma threat and control beliefs (i.e., putative mediators of behavior change). Guided by Protection Motivation Theory (Robberson and Rogers, 1998), **we hypothesize that behaviors and putative mediators will be higher in those who test, compared to those who decline testing or wait-list controls.**

Aim Ia. An important challenge of personal genomics involves the potential for those who receive “negative” genetic feedback to increase risky behaviors (McBride et al., 2010). To examine this potential unintended consequence of testing, we will conduct a subgroup analysis among those who receive average risk PGT-SC findings, examining sun protection at three months as the outcome. Predictors will include baseline skin cancer threat and control beliefs, skin cancer risk factors, and demographics. These findings will be used in future studies to develop messages for groups that receive average risk feedback, which accounts for large segments of those tested for moderate risk susceptibility factors across many diseases.

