In Phase II, patients will be eligible for the study if they have been registered at a UNM Clinic for six months and assigned a primary care provider, aged >18, and are fluent in either English or Spanish. We will exclude adults that are unable to consent, individuals who are not yet adults (infants, children, teenagers) and prisoners. Pregnant women will be eligible to participate. All participants in Phase II will be consented and interviewed at 1209 University Clinic, OSIS Orthopedic Clinic at [name], the Family Medicine Clinic, the Center for Employee and Occupational Health Services, both at [name] or the North Valley Clinic. Individuals who usually attend another UNM Clinic (Atrisco Heritage Center for Family and Community Health, Northeast Heights Clinic, North Valley Clinic, Westside Clinic, Southeast Heights Center for Family and Community Health, Family Medical Center, Lobo Care Clinic, Senior Health Center, or Southwest Mesa Center for Family and Community Health) and are accompanying a patient from these Clinics will be eligible for Phase II.

6) Number of Subjects (Recruitment Target)

Phase 1: We anticipate that we will conduct cognitive interviews of **40** subjects fluent in Spanish, 20 men and 20 women, who either completed high school or did not complete high school (see phase I recruitment table).

Phase I Recruitment Table

Gender

Education	Male	Female
Completed high school/equivalent or greater	10	10
Did not complete high school or equivalent	10	10

Usability Phase: We will conduct the usability survey in **up to 10** subjects who attend the 1209 Clinic.

Phase II: We anticipate that we will conduct a baseline assessment of **650** subjects (see SOMBRA Study Flow, p. 6). They will then be randomized to a “Wait List Control Group of **120** subjects and a PGT-SC group of **530** subjects. All **530** subjects will be offered MC1R genetic testing. The “Wait List Control Group (**120** subjects) will be offered the MC1R test after the **Three Month Follow Up Questionnaire**. Accordingly, all **650** subjects will be offered MC1R testing. Of those offered, based on our prior experience, we anticipate 30-50 percent will accept an invitation for testing.

Phase II: Recruitment Tables	Ethnicity	
	Hispanic	NHW
Waitlist Controls – n = 120	60	60
PGT-SC Group – n=530	265	265

7) Recruitment Methods

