C) Baseline Assessment. All participants approached will be asked to complete a three minute Eligibility Screening and a Screening Survey to determine their interest in and eligibility for study participation, as well as basic demographics. If they are eligible and interested in study participation, the PA will fully explain the study and the participant will provide written informed consent (Consent - Number 2 and UNMHSC_HIPAA_Authorization), receiving a copy of the signed consent form. The PA will guide them to complete the Baseline Questionnaire in the clinic in a semi-private space with dedicated study computer (tablet or laptop computer).

Based on prior research, we anticipate that 30% of those approached will participate and complete the Baseline Questionnaire. Sample size estimates indicate that a total number of participants of 885 is necessary to evaluate our outcomes.

After completion of the Baseline Questionnaire facilitated by the PA, participants will receive a \$15 Target Gift card for their time and effort. They will sign a Sombra Gift Card Form and receive a Sombra Appointment Card. They will then be randomized to Group 1 - wait-list controls or to Group 2 to consider PGT-SC through a secure website (randomized and balanced across Hispanic and Non-Hispanic ethnicity, n=120 in control arm, n=530 in PGT-SC arm). "Hispanic" ethnicity will be recorded by self-report. Patients will choose Spanish or English study materials.

D) PGT-SC Invitation. (Group 2 – n=530)

Participants randomized to the PGT-SC study arm will view materials on the SOMBRA Website via Internet from a home, work, library or community-based organization computer, or alternatively through a paper version of the modules if they prefer. Internet reach in Albuquerque is >80% and WiFi is available throughout the city. All participants will be asked to consider the four educational modules regarding PGT-SC. The PGT-SC modules are:

- 1) What genetic testing can and cannot tell you,
- 2) Skin cancer and genes,
- 3) Your rights if you take part in genetic research, and
- 4) Your decision to be tested or not.

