After each module, participants will be asked to answer a series of questions regarding knowledge and satisfaction with the content of each module, and after section 4 they will be asked to register a decision as to whether they wish to have a skin cancer genetic test, or not. Participants will only be able to register a test decision if they have already read and completed the questions on the first three educational modules. Knowledge and satisfaction questions are part of each module. Those who complete these steps will receive an additional \$5 target Gift card incentive for each module for a maximum a total of \$15 in Target Gift card incentives. There is no incentive associated with the 4th module on the decision to conduct genetic testing or not.

Registration of a test decision (yes; no) is our primary assessment of "reach" in this study. We expect a minimum of 30% of participants who complete the Baseline Survey to register a genetic test decision, and that this will reach 50% in some subgroups, including those with higher literacy. Additional assessments of "reach" include completion of the baseline survey and decision to pursue PGT-SC testing (yes; no).

Those who register a decision to proceed with testing will receive a DNA buccal cell test kit with instructions (Donor Mailing Form and Specimen Collection Form), which will allow them to provide a saliva sample for genetic testing, pre-paid postage envelope, and instructions in English and Spanish for buccal cell collection. Based on The Multiplex Study, we anticipate that up to 50% of participants who consider PGT-SC will return a saliva sample for genetic testing. The Molecular Epidemiology Laboratory at UNM HSC will conduct testing; participants will receive PGT-SC results by mail (or by email, if they prefer) within one month.

We will employ state-of-the-art methods of risk communication used with high comprehension in the Multiplex Study, guided by Co-Investigator [name], who originally developed Multiplex Study risk communication materials. These materials combine verbal and pictorial displays of risk information and denominator information. We will also provide written information to clarify risk level given that individuals tend to rely on the gist of the information provided (See SOMBRA Result A for average risk individuals and SOMBRA Result B for higher risk individuals)

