All subjects who participate in PGT-SC genetic testing will receive a telephone call two weeks after results are mailed, to assess PGT-SC result comprehension and potential distress (see Two Week Risk Feedback Comprehension Assessment) and to answer any questions they may have. All those who

complete this Assessment will receive a \$5 Target Gift card as thanks for their effort. Based on prior literature documenting low levels of distress in those undergoing genetic testing for high-risk mutations, and among those found to carry *CDKN2A* mutations, we anticipate low levels of distress regarding PGT-SC feedback. Anyone who reports high distress will be referred to Clinic Director and Co-Investigator [name], who addresses distress issues regularly in the UNM clinic. If they wish, a genetic counselor will be available.

E) Three-month follow-up.

All participants who completed Baseline Assessments (whether tested or not) will be contacted for assessment by telephone three months after PGT-SC testing (Three Month Follow Up Questionnaire). Participants who complete this three-month follow up assessment will receive a \$15 Target Gift card for their valued study participation.

F) Group 1 genetic testing option.

Those 120 participants randomized to the control group will receive an offer for PGT-SC directly after the three-month follow-up assessments. They will be offered testing, and of those who pursue testing, will receive results by mail or by email, sent by the PA who enrolled them, and a two-week follow-up telephone call to assess result comprehension and potential distress.

G) Summary.

We anticipate that patients will be enrolled over an approximately 12 month period, complete assessments and receive feedback within 20 months. Thus individuals are estimated to be in the study for 3 months and the enrollment and assessment period overall will last as long as 20 months total. Primary analyses will be completed in the 6 months following the 24 months period of participation; the entire study will take 3 years.

9) Study Endpoints.

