Test result comprehension includes recall, perceived clarity, interpretation and recall, believability, and test regret on closed, open-ended scales.	Adopted from the NHGRI Multiplex Study (Kaphingst 2012, McBride 2009).	Risk feedback comp. assessment
Cancer-related Distress is assessed through 7 items on separate 5-point scales (not at all-extremely).	Impact of Events Scale – Revised Intrusive thoughts subscale (Horowitz 1979) is widely used with good internal and test-retest reliability; good ability to distinguish those with cancer distress (Joseph 2000; Thewes 2001).	Risk feedback comp. assessment; 3-month
Demographics (birth year, US nativity, survey language choice, gender, education, income, race/ethnicity); Internet availability.	Standard demographic questions; Internet availability (Nelson 2004).	B
Melanoma risk factors (personal and family melanoma history; phenotype, sunburn hx).	Heavily used items from prior epidemiology research (Gandini 2005).	B

References for Endpoints:

Bandura A. *Social foundations of thought and action: a social cognitive theory*. Englewood Cliffs, NJ: Prentice-Hall; 1986.

Espinosa de Los Monteros K, Gallo LC. The relevance of fatalism in the study of Latinas' cancer screening behavior: a systematic review of the literature. *International journal of behavioral medicine*. Dec 2011;18(4):310-318.

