Overall data processing and missing data imputation. We will first examine aspects of data quality and distributional assumptions to ensure statistical integrity and accuracy: 1) data skewness, kurtosis, and parametric assumptions; 2) intention-to-treat (ITT) principles; 3) missing data considerations; and 4) control of potentially inflated Type-I errors due to multiple statistical tests. First, data skewness and kurtosis will be examined to determine whether each variable significantly deviates from normality. If so, we will employ data transformations by taking a log or square root of the skewed variables, or by using the Box-Cox transformation or kernel estimation techniques (Diggle et al., 2002) to determine the best-fitting parametric density. Second, we assume that up to 20% of the respondents will be unreachable at our three-month follow-up assessment; missing assessments may be amenable to imputation by several powerful techniques that can handle both continuous and categorical data (Graham et al., 2997; Schafer and Olsen, 1998). A related approach is the use of Hierarchical Linear Models (HLM) (Raudenbush and Bryk, 2002) to use all available behavioral outcomes data since HLM does not carry out list-wise deletion by default, thus the statistical power loss due to missing data may be minimal. We will apply the intention-to-treat (ITT) principle (Nich and Carroll, 1997). An ITT analysis in Aim I (Nich and Carroll, 1997; Willett et al., 1998) would assume missing data is related to lack of sun protection adherence. We may use the Pattern-Mixture Model to examine whether or not missed follow-up assessments are associated with baseline characteristics with safeguards to minimize

model overfit (Hedeker and Gibbons, 1997). Finally, to control for potentially inflated type-I error rate due to multiple comparisons, analyses can also incorporate a multiple comparisons method, such as a False Discovery Rate-controlling procedure, which is more powerful than simple Bonferroni corrections.

References for Data Processing

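### Aim Ia brings about 13-17 or more candidate predictors to roughly 64-106 average-risk recipients, with no selection or shrinkage rule and without naming baseline sun protection

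*Combined protocol and SAP*

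**What the plan says.** Section 3, Aim Ia, describes a subgroup analysis of participants who receive average-risk feedback, with sun protection at three months as the outcome. On the model it says only: "Predictors will include baseline skin cancer threat and control beliefs, skin cancer risk factors, and demographics". On use: "These findings will be used in future studies to develop messages for groups that receive average risk feedback".

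The content of the four domains has to be read from the measures table in section 9. Threat beliefs comprise three risk-perception measures on separate scales, plus worry. Control beliefs comprise self-efficacy and response-efficacy, seven items each. Risk factors are personal history, family history, phenotype and sunburn history. The last domain is "Demographics (birth year, US nativity, survey language choice, gender, education, income, race/ethnicity", with Internet availability in the same row. Sun protection is four behaviours on separate five-point scales, measured at baseline and three months, and no composite is defined.

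On numbers, section 8C gives "n=120 in control arm, n=530 in PGT-SC arm", and section 8F says that controls "will receive an offer for PGT-SC directly after the three-month follow-up assessments". Section 6 adds: "we anticipate 30-50 percent will accept an invitation for testing".

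Section 13 (overall data processing) lists control of Type I error among its general considerations and names a false discovery rate procedure, but as something the analyses may use. It defines no family of tests. Its one reference to overfitting, "with safeguards to minimize", belongs to the pattern-mixture model for missed follow-up.

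**The concern.** Aim Ia asks whether reassuring genetic feedback could lead people to protect themselves less, and the answer is meant to inform later messages. The analysis has many candidate predictors, a small subgroup, and no rule for choosing, combining or shrinking terms. Raw fit may then look better than it is, individual estimates will be imprecise, and an isolated significant predictor may not be distinguishable from chance. Moreover, a model of the three-month level that omits the baseline level describes who protects themselves less, not who has changed.

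**Working it through.** **The plan's own figure.** The only sample-size statement is 885 participants (sections 8C and 22). No alpha, power, effect size or standard deviation is given, so it cannot be reproduced. The arms sum to 120 + 530 = 650. No size is stated for the Aim Ia subgroup.

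**Subgroup size.** Only the 530-person arm contributes, because controls are offered testing after the outcome has been measured. The formula is n = 530 x share tested x share average-risk x share followed.

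- Share followed: 0.80 (section 13 allows up to 20% unreachable).
- Share average-risk: 0.50. This is an assumption. Section 4 says that half the general population carries at least one high-risk variant, but the rule for average-risk feedback is not defined.
- Share tested: 30-50% of those offered (section 6). Section 8D can be read more strictly: "We expect a minimum of 30% of participants who complete the Baseline Survey to register a genetic test decision", rising to 50% in some subgroups, with up to half of those who consider testing returning a sample. If that half applies only to people who register a decision, the share tested is 15-25%.

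Results:

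- 530 x 0.30 x 0.50 x 0.80 = 63.6; 530 x 0.50 x 0.50 x 0.80 = 106.
- Stricter reading: 530 x 0.30 x 0.50 x 0.50 x 0.80 = 31.8; 530 x 0.50 x 0.50 x 0.50 x 0.80 = 53.
- With an average-risk share of 40-60%, the extremes become 25 and 127.
- If 885 were enrolled, the range would be about 43 (same allocation: 885 x 530/650 x 0.30 x 0.50 x 0.50 x 0.80) to 153 (controls held at 120: 765 x 0.50 x 0.50 x 0.80).

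**Candidate predictors.** At one degree of freedom each: 3 risk perceptions + 1 worry + 2 control beliefs + 4 risk factors + 7 demographics = 17. With one threat score and one control score: 1 + 1 + 4 + 7 = 13. Internet availability, or dummy coding of race/ethnicity, education, income or phenotype, would raise either count.

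**Fit and precision when no association exists.** Expected R-squared is p/(n-1). With 17 predictors, the smallest partial correlation that reaches p<0.05 is t/sqrt(t^2 + n - 18), where t is the two-sided 5% critical value on n - 18 degrees of freedom. The plan states no alpha, so 0.05 two-sided is assumed.

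| n | People per predictor (17) | R-squared, p=17 | R-squared, p=13 | Smallest significant partial r (p=17) |
|---|---|---|---|---|
| 32 | 1.9 | 0.55 | 0.42 | 0.50 |
| 53 | 3.1 | 0.33 | 0.25 | 0.32 |
| 64 | 3.8 | 0.27 | 0.21 | 0.28 |
| 106 | 6.2 | 0.16 | 0.12 | 0.21 |

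**False positives.** With 17 unadjusted tests, 17 x 0.05 = 0.85 are expected. If the tests were independent, the chance of at least one is 1 - 0.95^17 = 0.58. In a simulation of ordinary least squares with all 17 null predictors entered together (4,000 runs per case, predictor correlation 0 and 0.3), the chance was 0.41-0.43 at n=32 and 0.54 at n=106. With Benjamini-Hochberg control it was about 0.04-0.05 throughout.

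**The case against.** The strongest reply is that the plan never commits to the model criticised here. Several stronger readings are tempting, and the documents do not support them.

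- A reader might infer that at least 17 predictors will be fitted together. Aim Ia names domains, and the measures table serves every aim. Composite scoring gives 13. What stands is that no rule limits the set.
- A reader might blame the small sample for false positives. In a standard linear model each null coefficient keeps its 5% error rate at any n, and the simulated chance is slightly lower at n=32 than at n=106. The number of tests drives false positives. The small sample inflates raw R-squared and widens intervals, so that only large estimates reach significance.
- A reader might conclude that significant predictors are certain to appear and will be largely chance. The unadjusted probability is near one half, and saying largely chance would require assuming that almost no true associations exist. Nor are coefficients biased in a pre-specified linear model. Under the null, adjusted R-squared averages about zero and the overall F test rejects about 5% of the time.
- A reader might multiply over the four sun-protection items: 68 tests and 3.4 expected false positives, with a chance of at least one above 90% if the outcomes were independent. Aim Ia speaks of sun protection as a single outcome and plans no four separate models. The missing composite leaves that possibility open, no more.

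The plan does mention Type I error control, and it would work if used. Because it is optional and not tied to Aim Ia, it cannot be counted as a safeguard, and it would not correct an inflated R-squared. Nothing in this trial's care or main comparisons depends on Aim Ia; its findings feed later studies. Finally, the predictor list is worded as open, so baseline sun protection is not excluded, only not named.

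**Conclusion.** The concern holds as a gap in specification. Aim Ia brings about 13-17 or more candidate predictors, with no selection or shrinkage rule, to roughly 64-106 people, or 32-53 on the stricter reading of kit return. At 64-106 people, 17 predictors leave 3.8-6.2 people each. Raw R-squared from noise alone would then average 0.16-0.27, and up to 0.55 at n=32; the claim that the model would look predictive therefore fits the low end best. The unadjusted chance of at least one false-positive predictor is about 41-58% per outcome, against about 5% with false discovery rate control.

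These sizes rest on the assumed 50% average-risk share, 20% loss, one degree of freedom per predictor and a two-sided 5% level. Separately, leaving baseline sun protection unnamed weakens the link between the analysis and the question of increased risky behaviour.

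**What to change.** Amend the Aim Ia analysis text as follows.

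1. Name baseline sun protection as a term in the model.
2. Define one pre-specified sun-protection composite as the outcome.
3. Either score threat, control beliefs and risk factors as one term each with a short pre-specified demographic set, or keep all candidates and use penalised regression.
4. Report bootstrap optimism-corrected fit.
5. Make false discovery rate control mandatory for the Aim Ia predictor tests, with the family defined.
6. Label the results hypothesis-generating.

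Shortening the list is not enough alone. With, for illustration, seven terms (baseline, three scores, three demographics), expected null R-squared is 7/105 = 0.07 at n=106 and 7/63 = 0.11 at n=64, but still 7/31 = 0.23 at n=32. The unadjusted chance of a false positive, if tests are independent, is 1 - 0.95^7 = 0.30. Hence items 4 and 5.

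The cost is analysis wording: no new data and no extra recruitment. With the scored set, individual items are no longer examined separately. The reported fit will look less favourable.

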In Phase II, patients will be eligible for the study if they have been registered at a UNM Clinic for six months and assigned a primary care provider, aged >18, and are fluent in either English or Spanish. We will exclude adults that are unable to consent, individuals who are not yet adults (infants, children, teenagers) and prisoners. Pregnant women will be eligible to participate. All participants in Phase II will be consented and interviewed at 1209 University Clinic, OSIS Orthopedic Clinic at [name], the Family Medicine Clinic, the Center for Employee and Occupational Health Services, both at [name] or the North Valley Clinic. Individuals who usually attend another UNM Clinic (Atrisco Heritage Center for Family and Community Health, Northeast Heights Clinic, North Valley Clinic, Westside Clinic, Southeast Heights Center for Family and Community Health, Family Medical Center, Lobo Care Clinic, Senior Health Center, or Southwest Mesa Center for Family and Community Health) and are accompanying a patient from these Clinics will be eligible for Phase II.

6) Number of Subjects (Recruitment Target)

Phase 1: We anticipate that we will conduct cognitive interviews of **40** subjects fluent in Spanish, 20 men and 20 women, who either completed high school or did not complete high school (see phase I recruitment table).

Phase I Recruitment Table

Gender

Education	Male	Female
Completed high school/equivalent or greater	10	10
Did not complete high school or equivalent	10	10

Usability Phase: We will conduct the usability survey in **up to 10** subjects who attend the 1209 Clinic.

Phase II: We anticipate that we will conduct a baseline assessment of **650** subjects (see SOMBRA Study Flow, p. 6). They will then be randomized to a “Wait List Control Group of **120** subjects and a PGT-SC group of **530** subjects. All **530** subjects will be offered MC1R genetic testing. The “Wait List Control Group (**120** subjects) will be offered the MC1R test after the **Three Month Follow Up Questionnaire**. Accordingly, all **650** subjects will be offered MC1R testing. Of those offered, based on our prior experience, we anticipate 30-50 percent will accept an invitation for testing.

Phase II: Recruitment Tables	Ethnicity	
	Hispanic	NHW
Waitlist Controls – n = 120	60	60
PGT-SC Group – n=530	265	265

7) Recruitment Methods

Phase I: Project Assistants (PAs) will approach primary care patients in the UNM 1209 clinic with a **Clinic Flyer** and **Phase I FAQ** for Clinic Patients explaining the main purpose of the study as well as eligibility requirements and the **NCI Skin Cancer Pamphlet in English or Spanish** (Spanish version; “Anyone can get skin cancer,” <https://pubs.cancer.gov/ncipl/detail.aspx?prodid=P237>). They will explain the study and review the **Information Sheet** document for Phase I. If the potential participant decides to participate, they will evaluate all materials (Clinic Flyer, FAQ for Clinic Patients, NCI Skin Cancer Pamphlet, Phase II Consent, Screening Survey, Refuser Survey, Baseline Questionnaire, Introduction Letters - Groups 1 and 2, Sombra Gift Card Form, Sombra Appointment Card, Sombra Website, Donor Mailing Instructions, Specimen Collection Instructions, Sombra Results A (for average risk feedback), Sombra Results B (for increased risk feedback), Two Week Risk Feedback Comprehension Questionnaire, and Three Month Follow Up Questionnaire) in a semi-private area of the Clinic.

Usability Phase: To conduct usability of the website, we will recruit up to 10 patients from our target population (1209 Clinic). 1209 clinic waiting room patients will be approached and invited to participate in the project usability testing of the website. The PA will explain the purpose of the SOMBRA website and of usability testing, and interested participants will be given an Information Sheet and usability testing will be conducted. Participants will be asked to use the website in the presence of a project assistant (PA), thinking out loud as they use it. The PA will observe participants and take notes on the problems identified in using the website, and then ask a brief set of questions about the website (See Usability Questions). The interaction will take approximately 45 minutes or less. The PA will summarize the results of the usability evaluation for each participant, and these results will be used for website improvement. Participants will receive a \$20 Target gift card for their valued time and effort.

Phase II: Clinic Flyers and NCI Skin Cancer Pamphlets in both English and Spanish will be available at various spots throughout the Clinic. All Staff will know about the study and be available to answer questions and help direct potential participants to the bilingual PAs. The PAs will approach primary care patients or a person accompanying them who attends another UNM Clinic (see above) in the UNM 1209 clinic, the OSIS Orthopedic Clinic, the Family Medicine Clinic, the Center for Employee or North Valley Clinic and Occupational Health Services with a Clinic Flyer and Phase II FAQ for Clinic Patients explaining the main purpose of the study as well as eligibility requirements and the NCI Skin Cancer Pamphlets (available in English and Spanish versions; “Anyone can get skin cancer,” <https://pubs.cancer.gov/ncipl/detail.aspx?prodid=P237>). They will explain the study and review the Informed Consent -2 and **UNMHSC_HIPAA_Authorization** documents. If the potential participant decides to enroll, they will then be given a Screening Survey and, if they decide not to enroll, a very

short Refuser Survey. If they decide to continue the PA will conduct a Baseline Questionnaire in a semi-private area of the Clinic.

8) Study Timeline

This study will take place in three phases:

Phase 1: Cognitive Interviews in Spanish.

Usability Phase: Testing usability of the website.

Phase II: Personalized Genomic Testing for Skin Cancer (PGT-SC).

Phase I Cognitive Interviews: Spanish Translation and PGT-SC Website launch (4-6 months). First, the MSKCC Linguistic and Cultural Competence Team ([name] and [name], Co-Investigators) within the Immigrant Health and Cancer Disparities Service at MSKCC will provide Spanish translations of all English **IRB approved** study materials with the assistance of [name] at UNM (Clinic Flyer, FAQ for Clinic Patients, (NCI Skin Cancer Pamphlet was translated by NCI), Consent – Number 2, Screening Survey, Refuser Survey, Baseline Questionnaire, Introduction Letter for Groups 1 and 2, Sombra Gift Card Form, Sombra Appointment Card, Sombra Website, Donor Mailing Instructions, Specimen Collection Instructions, Sombra Results A (for average risk feedback), Sombra Results B (for increased risk feedback), Two-Week Risk Feedback Comprehension Questionnaire, and Three Month Follow Up Questionnaire).

An amendment will be submitted to the IRB following cognitive interview assessments and results for approval of the Spanish translations prior to the use of these translated materials in Phase II. Our bilingual PAs will approach Spanish speaking primary care patients in 1209 clinic with the Clinic Flyer, the Phase I FAQ for Clinic Patients and NCI Skin Cancer Information Pamphlet in Spanish (“Anyone can get skin cancer,” <https://pubs.cancer.gov/ncipl/detail.aspx?prodid=P237>) and will conduct a series of up to 60 minute cognitive interviews with Phase 1 consented eligible participants to ensure the comprehensibility and acceptability of the translations in our Albuquerque population with 40 Spanish-speakers with balanced stratification across gender and education level (> high school; < high school). Co-Investigator [name], a genetic anthropologist with expertise in the cultural and genetic background of New Mexico Hispanics, will work with [name] (PA) to construct a series of questions to be included in the cognitive interviews to address Hispanic sociocultural issues relevant to skin cancer genetic testing; such questions will include: What comes to mind when you hear the term “skin cancer”? What comes to mind when you hear the term “genetic testing”? Would you want to have genetic testing for skin cancer? Why or why not? What would be your language preference if you were receiving genetic testing results? Who would you trust to give you information about genetic testing? These open-ended responses will be summarized and tabulated. [name] and the team will discuss the interpretation of the responses. Based on these findings, we will modify the information given to patients and in the surveys.

There will be web-based computer modules, providing genetic, skin cancer and MC1R educational materials and the testing invitation (Baseline Questionnaire) developed by [name] at Klein Buendel, Inc. (KB), in Colorado. [name] specializes in the development of health education programs and multimedia products in the areas of chronic disease prevention and control. The modules are: 1) What genetic testing can and cannot tell you, 2) Skin cancer and genes, 3) Your rights if you take part in genetic research, and 4) Your decision to be tested or not .The website contains four modules to include

[figure not shown]
comprehension questions “wrapped” inside a website interface. The interface will include help files, navigation devices, and data collection code. It will be tested in-house for code stability, and beta tested prior to exportation to the Web server at Klein Buendel. MSKCC and Klein Buendel will not have any access to PHI and will only receive de-identified data.

Usability Phase.

After website development, we will collect input from up to 10 patients from 1209 Clinic concerning website usability (overall look and feel and website functioning) to allow for any further website refinement prior to website launch.

Phase II Personalized Genomic Testing for Skin Cancer (PGT-SC, 20 months).

A) Clinic physician-provider study preparation. Prior to beginning the PGT-SC, study [name], Clinic Director and Co-Investigator, will conduct an in-service meeting with 1209 Clinic physicians and staff to introduce the study, discuss current state-of-the-science in skin cancer genomics, and provide them with brief written information. [name] will do the same for the Orthopedic Clinic the Family Medicine Clinic ,the Center for Employee and Occupational Health Services and the North Valley Clinic. This will allow physicians to respond to patient inquiries, as well as requests for skin cancer screening and genetic counseling. Detailed questions will be referred to Drs. [name] and [name]. [name], [name], [name], [name] or [name] xxxx will provide additional updates with physicians on request throughout the study.

B) Recruitment (See Figure Above, Study Flow). Our bilingual PAs will approach primary care patients or someone accompanying them who attends another UNM Clinic (see above) in 1209 Clinic, the Orthopedic Clinic, the Family Medicine Clinic, the Center for Employee and Occupational Health Services or the North Valley Clinic with the Clinic Flyer the Phase II FAQ for Clinic Patients, and the NCI Skin Cancer Information pamphlet (available in English and Spanish versions; “*Anyone can get skin cancer*,” <https://pubs.cancer.gov/ncipl/detail.aspx?prodid=P237>). They will determine if potential subjects are interested in participation.

C) Baseline Assessment. All participants approached will be asked to complete a three minute Eligibility Screening and a Screening Survey to determine their interest in and eligibility for study participation, as well as basic demographics. If they are eligible and interested in study participation, the PA will fully explain the study and the participant will provide written informed consent (Consent - Number 2 and UNMHSC_HIPAA_Authorization), receiving a copy of the signed consent form. The PA will guide them to complete the Baseline Questionnaire in the clinic in a semi-private space with dedicated study computer (tablet or laptop computer).

Based on prior research, we anticipate that 30% of those approached will participate and complete the Baseline Questionnaire. Sample size estimates indicate that a total number of participants of 885 is necessary to evaluate our outcomes.

After completion of the Baseline Questionnaire facilitated by the PA, participants will receive a \$15 Target Gift card for their time and effort. They will sign a Sombra Gift Card Form and receive a Sombra Appointment Card. They will then be randomized to Group 1 - wait-list controls or to Group 2 to consider PGT-SC through a secure website (randomized and balanced across Hispanic and Non-Hispanic ethnicity, n=120 in control arm, n=530 in PGT-SC arm). "Hispanic" ethnicity will be recorded by self-report. Patients will choose Spanish or English study materials.

D) PGT-SC Invitation. (Group 2 – n=530)

Participants randomized to the PGT-SC study arm will view materials on the SOMBRA Website via Internet from a home, work, library or community-based organization computer, or alternatively through a paper version of the modules if they prefer. Internet reach in Albuquerque is >80% and WiFi is available throughout the city. All participants will be asked to consider the four educational modules regarding PGT-SC. The PGT-SC modules are:

- 1) What genetic testing can and cannot tell you,
- 2) Skin cancer and genes,
- 3) Your rights if you take part in genetic research, and
- 4) Your decision to be tested or not.

After each module, participants will be asked to answer a series of questions regarding knowledge and satisfaction with the content of each module, and after section 4 they will be asked to register a decision as to whether they wish to have a skin cancer genetic test, or not. Participants will only be able to register a test decision if they have already read and completed the questions on the first three educational modules. Knowledge and satisfaction questions are part of each module. Those who complete these steps will receive an additional \$5 target Gift card incentive for each module for a maximum a total of \$15 in Target Gift card incentives. There is no incentive associated with the 4th module on the decision to conduct genetic testing or not.

Registration of a test decision (yes; no) is our primary assessment of "reach" in this study. We expect a minimum of 30% of participants who complete the Baseline Survey to register a genetic test decision, and that this will reach 50% in some subgroups, including those with higher literacy. Additional assessments of "reach" include completion of the baseline survey and decision to pursue PGT-SC testing (yes; no).

Those who register a decision to proceed with testing will receive a DNA buccal cell test kit with instructions (Donor Mailing Form and Specimen Collection Form), which will allow them to provide a saliva sample for genetic testing, pre-paid postage envelope, and instructions in English and Spanish for buccal cell collection. Based on The Multiplex Study, we anticipate that up to 50% of participants who consider PGT-SC will return a saliva sample for genetic testing. The Molecular Epidemiology Laboratory at UNM HSC will conduct testing; participants will receive PGT-SC results by mail (or by email, if they prefer) within one month.

We will employ state-of-the-art methods of risk communication used with high comprehension in the Multiplex Study, guided by Co-Investigator [name], who originally developed Multiplex Study risk communication materials. These materials combine verbal and pictorial displays of risk information and denominator information. We will also provide written information to clarify risk level given that individuals tend to rely on the gist of the information provided (See SOMBRA Result A for average risk individuals and SOMBRA Result B for higher risk individuals)

